### 5.2.3 *Relative day*

Relative days (DY) will be calculated according to the following rule:

- Concerned date < reference date: DY = concerned date – reference date
- Concerned date ≥ reference date: DY = concerned date – reference date + 1

The reference date is the date of first administration of study treatment (in the study and in each period).

### 5.2.4 *Analysis visits*

The analysis will use the visits indicated on the subject's eCRF, while for the time points related to study variables, vital signs, ECG, and lung function assessments a windowing approach will be used (see time window definitions below).

The screening value is the last available and non-missing value before Period 1, Day - 1. This value corresponds to the screening visit, except in case of retesting. Reason for this approach is the use of retest results for subject eligibility assessment.

	Statistical Analysis Plan	
CLI-05993AB6-06	Final Analysis	Final 1.0 of 05OCT2023

Unscheduled assessments will not be used in the analysis unless as screening value, or per time window definitions below.

The unscheduled assessments will be checked during the data review meeting before database lock, and any different approach to the rule defined above will be documented in the data review report.

Baseline is defined in section 5.2.2.

All scheduled and unscheduled assessments will be listed.

Early termination and follow-up visits will be listed only, unless otherwise specified.

The analysis visit labels will be assigned using the following rules:

- All planned screening, re-screening, eligibility recheck, etc. visits occurred during the screening phase will be presented as ‘Screening’.
- All planned visits occurred during a scheduled day, will be presented as ‘Day x’ (x = study day, e.g. ‘Day -1’, ‘Day 1’, etc.)
- Early termination visits will be presented as ‘Early Termination’
- Follow-up visits will be presented as ‘Follow-up’
- Unscheduled visits will be presented as ‘Unscheduled’ unless the decision to reallocate the visit is fully documented in the DRR. In case of reallocation, the unscheduled visit will be presented with the same label as the replaced planned visit (see rules above)
- Other visits not covered by the rules above will be presented using similar labels to the ones used in SDTM (XX.VISIT)

Except when defined by time windows, the analysis time point labels, if applicable, will be assigned using the following rules:

- Pre-dose time points will be presented as ‘Pre-dose’
- Time points expressed in minutes in SDTM will be presented as ‘Xmin’ (e.g.: ‘10min’, ‘30min’, ‘45min’, etc.)
- Time points expressed in hours in SDTM will be presented as ‘Xh’ (e.g.: ‘1h’, ‘12h’, ‘24h’, etc.)
- Time points expressed in ranges in SDTM will be presented using the same ranges (e.g.: ‘-75min-6h’, ‘Within 1.5h’, ‘0-12h’, etc.)
- Unscheduled time points will be blank unless the decision to reallocate the time point is fully documented in the DRR. In case of reallocation, the unscheduled time point will be presented with the same label as the replaced planned time point (see rules above)
- Other time points not covered by the rules above will be presented using similar labels to the ones used in SDTM (XX.XXTPT)

The analysis time point labels for study variables, vital signs, ECG parameters, and lung function parameters will be assigned using the following time windowing rules. All assessments, including unscheduled assessments, will be allocated to time windows. Tables will present the time windows as defined below and listings will present the time windows, as well as the eCRF time point labels.

	Statistical Analysis Plan	
CLI-05993AB6-06	Final Analysis	Final 1.0 of 05OCT2023

Allocation of time assessments will be done according to the following tables:

Study variables:

Analysis time point window	Target time after end of radiotracer inhalation per assessment day per period (minutes)	Time interval (minutes)
0 (immediately)	0	[0;7]
15min	15	[8;22]
30min	30	[23;45]
1h	60	[46;75]
1h 30min	90	[76;105]
2h	120	[106;135]
2h 30min	150	[136;165]
3h	180	[166;210]
4h	240	[211;360]

Vital signs and Electrocardiogram:

Analysis time point window	Target time after first dose (last inhalation) of study treatment per assessment day per period (minutes)	Time interval (minutes)
Pre-dose	<0	Last day 1 (or day 8), pre-dose assessment
5min	5	[0;10]
15min	15	[11;45]
1h 45min	105	[46;180]

Note: The reference time for Pre-dose is the first inhalation of study treatment per assessment day per period (minutes).

	Statistical Analysis Plan	
CLI-05993AB6-06	Final Analysis	Final 1.0 of 05OCT2023

Lung function:

Analysis time point window	Target time after first dose (last inhalation) of study treatment per assessment day per period (minutes)	Time interval (minutes)
Pre-dose	<0	Last day 1 (or day 8), pre-dose assessment
20min	20	[0;60]

Note: The reference time for Pre-dose is the first inhalation of study treatment per assessment day per period (minutes).

Per parameter and analysis window, the value closest to the target time will be used in analysis tables and figures, other values will only be listed. If more than one value is located at the same distance from the target, then the latest in time will be selected. The value latest in time will be identified using, in order of preference, the assessment time, the visit and time point label or the group identifier. Missing values are removed before the selection is made.

Partially missing assessment dates or times disabling allocation to analysis windows will not be imputed and thus these assessments will not be considered in the per-time point analysis, except for the derivation of the worst.

### 5.2.5 *Worst-case*

A worst-case analysis visit (presented in the analysis as ‘At Any Time Point’, or similar) will be created for parameters for which abnormalities are defined to summarise values considered as the worst-case.

The worst-case analysis visit will be derived within each treatment period, including scheduled and unscheduled assessments as well as the early termination and follow-up visit assessments. Only post-baseline assessments will be considered for the worst-case analysis visit.

## 5.3 IMPUTATION AND ROUNDING RULES

### 5.3.1 *Missing values*

No imputation of missing values will be done (i.e. observed cases analysis).

### 5.3.2 *Values below or above a threshold*

Safety values expressed as below (or above) the limit of quantification will be imputed by the value of the quantification limit itself. Listings will always show the non-imputed values.

	Statistical Analysis Plan	
CLI-05993AB6-06	Final Analysis	Final 1.0 of 05OCT2023

### **5.3.3 Rounding of derived variables**

Derived variables will be rounded at display level:

- AE duration will be presented with 1 decimal.
- Mean of duplicates/triplicates will be rounded to the nearest integer.  
Note: since the rounding is applied at display level, in the listings, the change from baseline could be slightly different to the listed value at time point t – baseline value
- Relative change from baseline will be presented with 1 decimal.
- Compliance will be rounded to 1 decimal.

### **5.3.4 Outliers**

Potential other outliers will be discussed during the review of the data by the Chiesi team. Decisions on whether values are to be excluded from the analysis will be fully documented in the Open-Label DRR.

## **5.4 PRESENTATION OF RESULTS**

### **5.4.1 Calculation of descriptive statistics and percentages**

For continuous parameters, full descriptive statistics will only be presented if there are at least 2 non-missing observations. Alternatively, only the number of non-missing data points and mean are shown.

Descriptive statistics will include the number of non-missing data points, the arithmetic mean, the standard deviation (SD), the median, minimum and maximum.

Descriptive statistics will additionally include 95% (or 90%) confidence interval (CI) on the mean (based on t-distribution, without continuity correction).

Mean, median, SD and CI will be presented with one more decimal place than the individual values, with a maximum of 4 decimal places. Minimum and maximum will be presented with the same number of decimal places as the individual values, with a maximum of 3 decimal places.

For graphs showing mean values, a 95% CI flag will be shown (based on t-distribution, without continuity correction).

For event-type data, the denominator will be all subjects in the analysis set and phase and period. All treatments will be shown, even if no events are present.

For tabulations by planned treatment, subjects who discontinued the study early will not be included in the denominator of the treatment periods they did not attend.

P-values will be presented with three decimal places (Note: Any p-value less than 0.001 will be presented as <0.001 and any p-value greater than 0.999 will be presented as >0.999), ratios with three decimal places and test statistics with two decimal places.

For frequency tabulations, missing values will not be included in the denominator count when computing percentages.

Percentages will be shown with one decimal place.

	Statistical Analysis Plan	
CLI-05993AB6-06	Final Analysis	Final 1.0 of 05OCT2023

#### **5.4.2      *Presentation of treatments***

The following treatment labels will be used in the tables, listings and figures:

- T: HFA-152a Propellant
- R: HFA-134a Propellant

When presented by treatment sequence:

- T-R
- R-T

If possible, the long labels (i.e. HFA-152a Propellant, HFA-134a Propellant, etc.) should be used for tables, listings and figures. If needed for layout purposes, the short labels (i.e. HFA-152a or T, HFA-134a or R) will be used instead.

Unless specified otherwise, an overall column, to summarise all subjects over treatments, will be presented only in tables showing data that are not affected by the study treatment, as well as in the AEs summaries. The overall column will be shown last.

#### **5.4.3      *Ordering in tables, listings and figures***

If the treatments are presented as columns, tables will be sorted by analysis visit and time point. Otherwise, tables will be sorted first by treatment, then by analysis visit and time point.

The treatments will be shown in following order: T, R.

In the analysis of general characteristics, results will be presented by sequence except where stated otherwise. For all other analyses (study variables, safety), results will be presented by treatment.

All listings will be ordered by subject and then by analysis visit and analysis time point window (chronologically), unless specified otherwise.

In tables and figures showing several parameters, each parameter will begin on a new page and parameters will be sorted alphabetically, within the parameter category if applicable.

#### **5.4.4      *Raw SAS output***

In addition to the statistical output as described in section 8, raw SAS output will be delivered in separate files as ‘Appendix to Table 14.x.x.x’ for all tables presenting inferential statistics. The layout of the appendices will be similar to the table (study identifier, SAS program name, production date, page count); presenting the raw SAS output in the body section.

	Statistical Analysis Plan	
CLI-05993AB6-06	Final Analysis	Final 1.0 of 05OCT2023

## **6. CHANGES TO THE PLANNED ANALYSIS**

### **6.1 CHANGES NOT COVERED BY PROTOCOL AMENDMENTS BEFORE UNBLINDING**

According to the study protocol, the statistical analysis of MCC variables in whole lung region would be required, but the MCC measurements done in the left lung can be biased due to an overlap of signal from the stomach; therefore, only the right whole lung should be considered and included in the statistical analysis of the MCC data (inferential and descriptive statistics). Moreover, differently from what stated in the study protocol, where descriptive statistics would be provided for the whole lung region only, descriptive statistics for PPR in right central lung region (%), PPR in right peripheral lung region (%), Right Central/Peripheral Ratio and AUC0-4H in right whole lung will be provided as well. Also the figures will be provided for PPR in right central lung region and PPR in right peripheral lung region, in addition to the PPR in the right whole lung.

	Statistical Analysis Plan	
CLI-05993AB6-06	Final Analysis	Final 1.0 of 05OCT2023

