8. STUDY ASSESSMENTS

The **primary objective** of this study is to assess the effect of multiple doses of the HFA-152a propellant and the HFA-134a propellant (when administered not in combination with active compounds) on MCC.

The MCC assessment will be performed on Day -1 and on Day 8 of each treatment period, as described in [Section 7.2.1](#).

The following **study variables** will be considered to **assess the primary objective** of the study:

- MCC rate, as assessed by the percent particle retention at 2 hours after the inhalation of radiolabelled particles (PPR₂);
- MCC rate, as assessed by the percent particle retention at 4 hours after the inhalation of radiolabelled particles (PPR₄).

Note: PPR in whole lung will be used for the assessment of the variables above.

The following **study variable** will **complete the evaluation of the primary objective** of the study:

- MCC, as assessed by the area under the tracheobronchial particle retention curve between 0 and 4 hours (AUC₀₋₄) after the inhalation of radiolabelled particles.

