12.3.3 STUDY VARIABLES

MCC variables (in whole lung) evaluating the primary objective of the study (see [Section 8](#)) will be analysed in the ITT and PP sets, as follow:

- The change from baseline in PPR₂ at Day 8 will be analysed using an analysis of covariance (ANCOVA) model, including treatment, subject and period as fixed effects, and PPR₂ at Day -1 as a covariate. The adjusted mean change from baseline obtained with each treatment and the adjusted mean difference between HFA-152a and HFA-134a with their 95% confidence intervals (CIs) and p-values will be estimated by the model;
- The change from baseline in PPR₄ at Day 8 will be analysed using the same model used for the change from baseline in PPR₂.

The MCC variable completing the evaluation of the primary objective will be analysed as follow:

- The change from baseline in AUC₀₋₄ after the inhalation of radiolabelled particles will be summarised using descriptive statistics.

Descriptive statistics will also be provided for the MCC data (in whole lung) collected at all other post-dose timepoints (see [Section 7.2.1](#)).

Figures will be provided for the mean change from baseline in PPR (in whole lung), by treatment arm and each post-dose timepoints.

Data of other MCC parameters (i.e. MCC on central region and on peripheral region, and central/peripheral ratio, see [Section 7.2.1](#)) will be listed only.

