#### 2.1.2 *Endpoints and derivation rules*

- 1) Change from baseline in PPR2 (right whole lung) at Day 8
- 2) Change from baseline in PPR4 (right whole lung) at Day 8
- 3) AUC0-4: Area Under the Tracheobronchial Particle Retention Curve Between 0 and 4 hours after the inhalation of radiolabelled particles (to be calculated only for PPR parameter on right whole lung region)

The area under the result vs. time curve observed from time 0 up to the last measurable value (i.e., 4h) will be computed using the linear trapezoidal rule.

The change from baseline in area under the curve (AUC) normalised by time will be calculated as follows, using the trapezoidal summation rule:

- AUC0-4 normalised by time =

$$\left\{ \sum_i [(t_i - t_{i-1})(PPR_i + PPR_{i-1})/2] \right\} / \text{time}$$

- Change from baseline in AUC = AUC0-4 normalised by time at Day 8 – baseline (AUC0-4 normalised by time at Day -1).

	Statistical Analysis Plan	
CLI-05993AB6-06	Final Analysis	Final 1.0 of 05OCT2023

where:

- $t_0$  is the actual time of administration of radiotracer,
- for  $i = 15 \text{ min}, 30 \text{ min}, 1\text{h}, 1.5\text{h}, 2\text{h}, 2.5\text{h}, 3\text{h}, \text{ and } 4\text{h}$ ,  $PPR_i$  is the actual PPR value at each time point and  $t_i$  is the actual time of sample  $i$ .
- $time$  is the actual elapsed time from  $t_0$  until  $t_{4h}$ .

Per analysis window, only the time point closest to the target time will be considered for AUC calculation (as per analysis windows rules reported in section 5.2.4).

The following rules will be applied for the  $AUC_{0-4h}$  calculation:

- In case the last measurement for the  $AUC_{0-4h}$  (i.e. 4h) is missing, the entire curve will be considered missing;
- Single, isolated missing values (different from 0h or last value) will be replaced by linear interpolation using adjacent values;
- In case of two or more consecutive missing time points, the entire curve will be considered missing;
- In case of three or more missing time points, the entire curve will be considered missing.

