### 2.1.4 *Presentation of results*

All MCC variables in right whole lung (PPR in right whole lung region (%), PPR in right central lung region (%), PPR in right peripheral lung region (%) and Right Central/Peripheral Ratio) (including  $AUC_{0-4}$  only for right whole lung region) will be summarised by means of descriptive statistics by treatment. Actual values (with their 95% CI) and changes from baseline (with their 95% CI) will be tabulated separately.

The ANCOVA model will be performed for change from baseline of  $PPR_2$  and  $PPR_4$  at Day 8. The results will be tabulated, including the estimates (mean, 95% CI, p-value) of the model estimated changes from baseline and difference between HFA-152a and HFA-134a in change from baseline.

Graphs of the mean actual values and the mean changes from baseline over time will be prepared for PPR (in right whole lung region, right central lung region and right peripheral lung region) by treatment.

All MCC data will be listed. All MCC data for the whole and the left lung will be listed only.

	Statistical Analysis Plan	
CLI-05993AB6-06	Final Analysis	Final 1.0 of 05OCT2023

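### The SAP moves PPR2 and PPR4 from whole lung to right lung, and no planned output then estimates the whole-lung treatment difference that the protocol specifies.

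*SAP*

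**What the plan says.** Protocol Section 8 names PPR2 and PPR4 as the variables for the primary objective and adds: "PPR in whole lung will be used for the assessment of the variables above". Protocol 12.3.3 plans the ANCOVA, in the ITT and PP sets, for "MCC variables (in whole lung) evaluating the primary objective of the study". It also plans whole-lung descriptive statistics and figures.

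The SAP lists no protocol amendment. Its Section 2.1.2 defines both endpoints, and AUC0-4, on the right whole lung. Section 6.1 gives the reason, that "the MCC measurements done in the left lung can be biased due to an overlap of signal from the stomach", and concludes: "therefore, only the right whole lung should be considered and included in the statistical analysis of the MCC data". On the remaining data, SAP 2.1.4 states: "All MCC data for the whole and the left lung will be listed only".

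**The concern.** The two variables that carry the primary objective are redefined between the protocol (16 February 2023) and the SAP (5 October 2023), and the protocol's version gets no model, summary table or figure. A reader of the report could not see whether the change of region alters the comparison of the propellants.

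This matters more than usual here for two reasons. The trial is open-label, so the date of a SAP change does not by itself show that treatment results were out of sight. The study also asks whether a new propellant has an unwanted effect on clearance (Protocol 1.2), so an analysis that happens to show a smaller difference is the reassuring one.

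**Working it through.** The plan has no figure of its own to reproduce on this point. Protocol 12.1 says that no formal sample size calculation was made, and no effect size, SD or margin is given. The check is mainly a comparison of texts.

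**1. What each document plans**

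| Item | Protocol | SAP |
|---|---|---|
| Region for PPR2, PPR4 | Whole lung (8, 12.3.3) | Right whole lung (2.1.2) |
| ANCOVA, ITT and PP | Whole lung (12.3.3) | Right whole lung only (8.1, Tables 14.2.1.3.1, 14.2.1.3.2, 14.2.1.4.1, 14.2.1.4.2) |
| Descriptive statistics and figures | Whole lung (12.3.3) | Right lung: whole, central and peripheral (2.1.4, 6.1) |
| PPR baseline | Day -1 value | Day -1 value, defined for right lung only (5.2.2) |
| Whole-lung values | Analysed | Listed only (2.1.4) |
| Whole-lung change from baseline | Analysed | Not listed: Listing 16.2.6.1 gives changes for the right lung only (8.2) |

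The protocol's term cannot be read as already meaning the whole area of the right lung. SAP 6.1 itself treats the move as a departure from the protocol.

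**2. What follows.** The protocol's result is the adjusted whole-lung difference between propellants, with its 95% CI and p-value. No table, figure or listing in SAP Section 8 contains it or the individual changes it is built from. Individual whole-lung values are listed, so someone could derive it, but nobody is asked to.

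**3. Timing.** The heading of SAP 6.1 places the change before unblinding. Protocol 12.3 requires the SAP to be final before database lock. Protocol 6.6 says that the study is open-label and that the CRO and the site receive the randomisation list. There is therefore no unblinding event to come before, and lock does not rule out earlier sight of MCC data by treatment. Neither document dates the choice of region relative to the MCC data.

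**4. How large could a selection effect be? Illustration only.** The correlation between regions is assumed; the documents give none.

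- Whole lung contains right lung. If left and right have equal weight and variance and correlation rho, then corr(right, whole) = sqrt((1 + rho)/2). For rho = 0.5 this is sqrt(0.75) = 0.87; for rho = 0.9 it is sqrt(0.95) = 0.97. A value as low as 0.7 would need rho = 2 × 0.49 − 1 = −0.02, that is, unrelated lungs in one subject. Extra noise in the left lung would lower the correlation.
- The expected lower of two standard normal estimates with correlation r is −sqrt((1 − r)/π). At r = 0.866 this is sqrt(0.134/3.1416) = 0.21 standard errors; at r = 0.975 it is sqrt(0.0253/3.1416) = 0.09.
- With 18 complete subjects the standard error is about sqrt(2/18) = 0.33 residual SD, so the shift is 0.21 × 0.33 = 0.07 down to 0.09 × 0.33 = 0.03 residual SD. The model has 36 − 1 − 1 − 1 − 17 − 1 = 15 error degrees of freedom, so the 95% CI half-width is 2.131 × 0.333 = 0.71 residual SD. The shift is about 4% to 10% of that.
- Simulated paired t-tests (n = 18, two-sided 0.05, 100,000 runs, equal true effect and variance in both regions) give:

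| Assumed r | Regions disagree on significance, no true effect | Either significant, no true effect | Both significant, each with about 80% power |
|---|---|---|---|
| 0.80 | 5.8% | 7.8% | 72.6% |
| 0.90 | 4.3% | 7.2% | 75.1% |
| 0.95 | 3.1% | 6.6% | 76.7% |

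The third column is the false-positive rate if the more significant region were reported. The last is the power left if the less significant one were.

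**The case against.** The strongest defence is that this is a measurement correction made openly. The SAP reports it in the section meant for such changes and gives a credible physical reason. The same section adds central and peripheral right-lung summaries and figures, where the protocol would only have listed those regions. The study is described as exploratory, with no margin or success criterion. All of this stands, and it is why right lung should remain the main analysis.

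A second objection is that a whole-lung analysis cannot settle the matter. Whole-lung PPR includes the left-lung counts that the SAP distrusts, so a disagreement could come from stomach signal as easily as from selection. That also stands. Agreement would reassure; disagreement would have more than one explanation. It limits what the added analysis can show, but is no reason to leave the protocol's result unestimated.

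A third objection concerns the illustration. It treats one direction as favourable, while SAP 2.1.3 specifies two-sided tests. If favourable means closer to no difference, the expected signed shift under no true effect is zero and only the absolute size shrinks. That is correct, and is one more reason to treat the figures as a rough scale.

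A reader might infer that the region was picked after seeing results by propellant, or that the documents are silent on timing. Neither is supported. No passage shows that anyone had compared MCC results by treatment. The SAP 6.1 heading and the requirement to finalise before lock do address timing, though weakly in an open-label trial.

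**Conclusion.** The point holds as one of traceability and completeness. Both variables for the primary objective move from whole to right lung without an amendment, and no planned output estimates the protocol-specified treatment difference. This follows from the text alone and needs no numerical assumption.

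Its effect on the conclusion is unknown. Under the assumptions above, choosing the region with results in view would move the estimate by about 0.09 to 0.21 standard errors. That is small beside the confidence interval, and it describes what selection could do; it is not evidence that selection took place. Nor do the documents support calling the right-lung choice wrong. The change is worth making because it is cheap and lets readers see both results.

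**What to change.** Keep the right-lung ANCOVA as the main analysis, and make these changes to the SAP:

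- **2.1.3 and 8.1:** add the same ANCOVA on whole-lung PPR2 and PPR4, in the ITT and PP sets, as a supportive sensitivity analysis shown beside the right-lung tables. Two variables × two sets = four models and four tables. Align 2.1.4 and 6.1.
- **5.2.2:** define the whole-lung PPR baseline as the matched Day -1 time point of each period.
- **8.2, Listing 16.2.6.1:** add whole-lung changes from baseline.
- **Table footnote:** say that whole-lung values may include stomach signal, so agreement is reassuring and disagreement has more than one explanation.
- **6.1 (helpful, but secondary):** state when and on what basis the region was chosen, and who then had access to MCC data by treatment. If access cannot be ruled out, say so.

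The cost is four tables, a few derivation rules and a result that needs careful reading. SAP 2.1.1 already plans to collect whole-lung values, and SAP 9.1 already gives example model code. If the database is already locked, the same tables can go in the study report, labelled as the analysis that the protocol specified.
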